#### 12.3.1 Study Populations

Three populations will be employed in the analysis of study data:

- The **intent-to-treat (ITT)** population will consist of all subjects who have received at least one dose of study drug. All safety analyses will be performed on the ITT population.
- The **PK** population will consist of all subjects who receive at least one dose of study drug and have sufficient post-dose blood samples to obtain PK parameters.
- The **PD** population will consist of all subjects who receive at least one dose of study drug and have post-dose PD data available.

Primary safety analyses will be performed on the ITT population. Demographics, subject disposition, and screening and baseline characteristics will be summarized for the ITT, PK, and PD populations, where appropriate.

### **12.3.2 Subject Accountability, Demographics, and Baseline Characteristics**

Subject disposition, demographic information and baseline characteristics will be presented. Any discrepancy between treatment to be given and treatment received will be accounted for in these displays.

### **12.3.3 Concomitant Medications**

Concomitant medications will be coded using WHO Drug Dictionary (WHO-DD March 2013, Type B2 or later) and the data will be summarized and presented in tables and listings.

## **12.4 Planned PK Analysis**

Study drug concentrations will be used to calculate the following PK parameters:  $t_{1/2}$ ,  $C_{max}$ ,  $T_{max}$ , and  $AUC_{0-24}$  and  $AUC_{0-\infty}$ . PK parameters will be determined using noncompartmental method(s). Descriptive statistics of PK parameters for SYNT001 will include mean, SD, coefficient of variation (CV), median, minimum, and maximum.  $T_{max}$  will be reported as median and range. All descriptive statistics will be performed on untransformed PK parameters and after  $\log_{10}$  transformation of PK parameters.

For calculation of mean concentrations and generation of mean concentration-time profiles, all below the limit of quantification (BLQ) values will be set to zero except when an individual BLQ falls between 2 quantifiable values, in which case it will be omitted.

If there are values above the BLQ, but too sparse to allow full analysis, descriptive statistics will be performed on available values.

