Methodology	
Two cohorts of 8 eligible subjects each will receive 5 once-weekly 60-minute infusions of SYNT001 in planned doses of 10 mg/kg or 30 mg/kg. Based on review of safety, PD, and clinical outcomes of these 2 cohorts, a third cohort of up to 8 subjects may be treated at another dose, with a maximum dose of 45 mg/kg, but may also be lower than 10 mg/kg or between 10 and 30 mg/kg, inclusive.
 
  
 Cohort	No. of subjects	Dose	
   
 1	8	SYNT001 10 mg/kg	
 
 2	8	SYNT001 30 mg/kg	
  
 
Cohorts will be dosed sequentially beginning with Cohort 1. The first 2 subjects will be dosed at least 24 hours apart. A review of the 24-hour safety data for the first subject will be performed to ensure that there are no overt safety concerns before dosing the second subject. A review of the 7-day safety data for the first 2 subjects will be performed prior to dosing the remaining 6 subjects in the cohort. This evaluation will include a review of AE/SAE reports, vital sign assessments, physical examinations, ECGs, and clinical laboratory testing. The seriousness, severity, and relatedness of AEs/SAEs will also be considered in the safety evaluation. Safety data will be reviewed on a continuous basis throughout the study. All safety data and any available and relevant PD data through Day 42 (2 weeks after the last subject's last dose in Cohort 1) will be reviewed by a dose escalation committee before Cohort 2 is initiated. Escalation to Cohort 2 will proceed if there are no concerning safety signals and the review of available and relevant PD data supports advancing to a higher dose. The dose for Cohort 2 will be finalized after review of the safety and PD data, but will not exceed 30 mg/kg. Cohort 2 and Cohort 3, if added, will be dosed per the same schedule as Cohort 1.
 
On days where study drug is administered, vital sign and pulse oximetry measurements will be collected immediately prior to the infusion; 15, 30, and 45 minutes after the start of the infusion; at completion of the infusion; and 30 minutes, 1 hour and 2 hours following completion of the infusion.
 
On Days 0 and 28, PK blood samples will be collected prior to infusion start and then over the subsequent 48 hours. Subjects will remain at the clinic through the
	Cohort	No. of subjects	Dose	1	8	SYNT001 10 mg/kg	2	8	SYNT001 30 mg/kg

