## 12 STATISTICAL CONSIDERATIONS

All descriptive and inferential statistical analyses will be performed using the most recently released and available Statistical Analysis System (SAS) software, unless otherwise noted. Missing data will not be imputed unless otherwise stated. All clinical data captured will be provided in data listings. A Statistical Analysis Plan (SAP) and a Pharmacokinetic Analysis Plan (PAP) will be finalized prior to database lock.

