### 12.2 Sample Size Justification

Formal sample size calculations were not performed. The number of subjects was chosen based on feasibility and was considered sufficient to meet the study objectives.

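### Section 12.4 applies the CV to log10-transformed PK parameters, where it depends on the reporting unit and measures nothing; the log-scale summary should be the geometric mean and geometric CV

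*Protocol*

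**What the plan says.** Section 12.4 of the protocol names the PK parameters (half-life, Cmax, Tmax and two AUCs) and then the statistics: "Descriptive statistics of PK parameters for SYNT001 will include mean, SD, coefficient of variation (CV), median, minimum, and maximum". One parameter is treated separately: Tmax "will be reported as median and range". The section continues: "All descriptive statistics will be performed on untransformed PK parameters and after" log10 transformation of those parameters.

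The statistical methods part of the synopsis carries the same list and the same instruction. Neither place mentions a geometric mean, a geometric CV or a back-transformation, and Section 12.4 sets no reporting unit.

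**The concern.** The instruction covers every statistic in the list, and the CV is one of them. A CV is meaningful for a positive quantity on a scale with a true zero, because a change of unit multiplies the SD and the mean by the same factor. Logged values have no such zero. A change of unit shifts their mean and leaves their SD alone, so their ratio follows the choice of unit as well as the spread between subjects.

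PK is the first-listed secondary objective (Section 3.2), and the descriptive summaries are all the PK analysis that Section 12.4 sets out. A log-scale row with a CV of a few percent, printed near an untransformed CV of about 30%, invites the reading that the parameter hardly varies between subjects. The useful log-scale summaries, the geometric mean and geometric CV, are never named.

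**Working it through.** **Inputs from the protocol.** The list of statistics and the two scales come from Section 12.4 and the synopsis. The cohort size of 8 comes from the synopsis ("Two cohorts of 8 eligible subjects each will receive 5 once-weekly 60-minute infusions of SYNT001"). The protocol states no PK CV and no PK values, so there is no figure of its own to reproduce.

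**Assumptions, not in the documents.** Lognormal parameters; geometric CV of 30%, with 20% and 50% as the range; the geometric means shown in the table.

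**Effect of a unit change.** Replace x by c·x:

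- Untransformed: SD and mean are both multiplied by c, so SD/mean is unchanged.
- log10: the SD is unchanged and the mean becomes mean + log10(c), so SD/mean changes. It is undefined when the mean log is 0 (geometric mean of one unit) and negative below that.

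**Spread on the log10 scale for a geometric CV of 30%.** SD of ln x = sqrt(ln(1 + 0.30²)) = 0.2936. SD of log10 x = 0.2936 / 2.3026 = 0.1275.

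**Log-scale CV = 0.1275 / mean of log10 values:**

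| Assumed geometric mean | Mean of log10 | Log-scale CV |
|---|---|---|
| AUC 20,000 ug.h/mL | 4.301 | 3.0% |
| same, as 20 mg.h/mL | 1.301 | 9.8% |
| Cmax 200 ug/mL | 2.301 | 5.5% |
| same, in ng/mL | 5.301 | 2.4% |
| same, in mg/mL | −0.699 | −18.2% |
| Half-life 48 h | 1.681 | 7.6% |
| same, as 2 days | 0.301 | 42.4% |
| Half-life 24 h, as 1 day | 0 | undefined |

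**Range for the AUC example.** A geometric CV of 20% gives an SD of log10 of 0.0860, hence 0.0860/4.301 = 2.0% in ug.h/mL and 0.0860/1.301 = 6.6% in mg.h/mL. A geometric CV of 50% gives 0.2052, hence 4.8% and 15.8%.

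**What stays valid.** For 8 values placed at lognormal quantiles with a geometric CV of 30%, the untransformed CV is 29.4% in every unit tried and the SD of log10 is 0.1275 in every unit. The geometric CV follows from that SD: sqrt(exp((2.3026 × 0.1275)²) − 1) = sqrt(exp(0.0862) − 1) = 30.0%, again in every unit. The same formula returns 20.0% from 0.0860 and 50.0% from 0.2052.

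**The case against.** The strongest reply is that the same sentence also orders the ordinary CV on untransformed parameters, which is valid and independent of the unit. It orders the log10 SD too, from which the geometric CV follows directly. That stands, and it limits the point: the defect is one meaningless statistic beside sound ones.

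A second reply is that summaries after log transformation may be shorthand for back-transformed geometric summaries, and that the formula belongs in a later plan: "A Statistical Analysis Plan (SAP) and a Pharmacokinetic Analysis Plan (PAP) will be finalized prior to database lock". The unseen PK plan may indeed define it properly. But the protocol offers no such definition. It puts the CV in the list and applies the whole list to the log scale, so this is a stated rule that yields an invalid number and not a detail left open. Section 12.3 lets the SAP change the protocol's plans but asks for deviations to be described and justified, so it is simpler to correct the sentence itself.

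A third reply is that no decision in the trial rests on this number. That stands. Escalation uses safety and PD data (Section 8.4.1), Section 12.8 plans no statistical analysis to support it, and no sample size uses a PK CV ("Formal sample size calculations were not performed").

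It is also fair to say that the most extreme figures in the table arise where the chosen unit puts the geometric mean at or near one. The protocol prescribes no such unit.

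**Conclusion.** Section 12.4 and the synopsis are wrong as written on one statistic. The CV of log10-transformed PK parameters depends on the reporting unit, can be negative or undefined, and does not describe relative variability. Under an assumed geometric CV of 30%, the AUC example shows 3.0% or 9.8% depending on the unit. These sizes rest wholly on assumed PK values; the dependence on the unit is algebra and does not.

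A reader might infer that PK variability as a whole would be misreported, or understated about tenfold. The documents do not support that. The untransformed CV is ordered in the same sentence and would show about the right figure, and the log10 SD is sound. Tmax is arguably exempt, since it is to be given as median and range only. The primary safety objective and dose escalation are not affected. This is a reporting correction, worth making because it costs almost nothing.

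**What to change.** Change the sentence in Section 12.4 and in the synopsis together, to this effect: PK parameters other than Tmax will be summarised on the untransformed scale by mean, SD, CV, median, minimum and maximum; Tmax will be given as median and range only; from the log10 scale, the geometric mean, 10^(mean of log10 values), and the geometric CV, sqrt(exp((ln 10 × SD of log10 values)²) − 1), will be reported; no SD/mean CV will be calculated on log-transformed values.

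There is no need to move from log10 to natural logs, because the formula gives the same geometric CV. The PK analysis plan should use the same definition. The cost is one sentence in two places, with no new data and no change to trial conduct.

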## **12.5 Safety Data**

Safety observations and measurements include AEs, safety laboratory tests, vital sign measurements, PEs, and ECGs.

Treatment-emergent AEs will be summarized using the Medical Dictionary for Regulatory Activities (MedDRA®; Version 19 or higher) System Organ Class (SOC) and preferred term, classified from verbatim terms. The incidence and percentage of subjects with at least 1 occurrence of a preferred term will be included, using the most severe grade. The number of events per preferred term will also be summarized. Causality (relationship to study treatment) will be summarized separately.

AEs, SAEs, and AEs leading to withdrawal, dose modification, or treatment discontinuation will be listed by subject, cohort, and overall per SOC and preferred terms. Duration of AEs will be determined and included in listings, along with action taken and outcome.

Laboratory results will be summarized by cohort. Incidence of laboratory abnormalities will be summarized. The worst on-study grade after the first dose of study drug will be summarized. Results for variables that are not coded will be presented in the listings as below, within, and above the normal limits of the local laboratory.

Vital sign measurements and change from baseline will be summarized at each scheduled time point by cohort using descriptive statistics.

Arithmetic mean of parameters from triplicate ECG will be calculated first for each participant at each planned time point. Then summary statistics of ECG test parameters (mean of triplicate) and change from baseline to each post-dose time point will be calculated. Shift tables for ECG test result category change (normal, abnormal, clinically abnormal) from pre-dose to each post-dose time point showing number and percentage of subjects with movement between categories will be presented by treatment group. Frequency and percentage of subjects experiencing potential QTc prolongation ( $QTcF > 450$ ) will be summarized at each time point by cohort.

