Objective	Endpoint																				
Primary																					
Safety and tolerability of 5 once-weekly IV infusions of SYNT001 to subjects with pemphigus vulgaris or foliaceus	AEs and clinical (safety) laboratory tests																				
Secondary																					
PK of SYNT001 following a 1-hour IV infusion	PK parameters: $t_{1/2}$ , $C_{max}$ , $T_{max}$ , $AUC_{0-24}$ , and $AUC_{0-\infty}$ .																				
Effect of 5 once-weekly IV doses of SYNT001 on: 
 
Total IgG (IgG1-4), IgA, IgM, and albumin
 
Serum anti-Dsg (1 and 3) antibodies
 
	Changes in levels of IgG, IgG subtypes (IgG1-4), IgA, IgM, albumin, serum anti-Dsg (1 and 3) antibodies																				
Assess immunogenicity	Anti-SYNT001 antibodies																				
Disease Activity	PDAI Scores																				
Exploratory																					
Effect of 5 once-weekly IV doses of SYNT001 on biomarkers including: 
 
CIC
 
C3
 
Serum anti-epithelial cell antibody (AECA) levels
 
Exploratory biomarkers (FCGR2A SNP, RNAseq, urine IgG)
 
Immune phenotyping by flow cytometry
 
	Changes in CIC; C3; AECA levels by indirect immunofluorescence; FCGR2A SNP; RNAseq; urine IgG, CD3 + CD4 + T, CD3 + CD8 + T, monocytes, NK cells and B cells; urine IgG levels; changes in blood transcriptome																				

 
• Exploratory biomarkers to investigate immune response associated with pemphigus
 
	
Concomitant Treatment	Corticosteroid use during the study
SYNT001 levels in skin biopsies	Measures of SYNT001 levels in skin biopsies

Treatment-emergent AEs (TEAEs) will be summarized using the Medical Dictionary for Regulatory Activities (MedDRA®; Version 19 or higher) System Organ Class (SOC) and preferred term, classified from verbatim terms. The incidence and percentage of subjects with at least 1 occurrence of a preferred term will be included, using the most severe grade. The number of events per preferred term will also be summarized. Causality (relationship to study treatment) will be summarized separately.

TEAEs, SAEs, and AEs leading to withdrawal, or treatment discontinuation will be listed by subject, and cohort using SOC and preferred terms. Duration of AEs will be determined and included in listings, along with action taken, and outcome.

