Laboratory results will be summarized by time point and cohort. The incidence of laboratory abnormalities will be summarized. The worst on-study grade after the first dose of study drug will be summarized. Results for variables that are not coded will be presented in the listings as below, within, and above the normal limits of the central laboratory. Vital sign measurements will be summarized by cohort at each scheduled time point using descriptive statistics.

Study drug concentrations will be used to calculate the following PK parameters:  $t_{1/2}$ ,  $C_{max}$ ,  $T_{max}$ , and area under the curve (AUC). PK parameters will be determined using non-compartmental method(s). Descriptive statistics of PK parameters for SYNT001 will include mean, standard deviation (SD), coefficient of variation (CV), median, minimum, and maximum.  $T_{max}$  will be reported as median and range. All descriptive statistics will be performed on untransformed PK parameters and after  $\log_{10}$  transformation of PK parameters.

PD results will be summarized by cohort. Descriptive statistics of PD parameters for SYNT001 will include mean, SD, CV, median, minimum, and maximum.

Immunogenicity results will be summarized by cohort. Descriptive statistics will include mean, SD, CV, median, minimum, and maximum.

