### 6.7 Clinical Laboratory Measurements

Collection time for all safety, PD, and exploratory labs are outlined in [Table 1](#).

Laboratory testing (hematology, urinalysis, serum chemistry, virology, serology, pregnancy tests, PD samples, PK samples, and anti-drug antibody samples) will be performed using established methods by a central laboratory. Safety laboratory panels are defined as listed in Table 3. Blood and urine samples for hematology, serum chemistry, and urinalysis will be prepared using standard procedures. Results will be provided to the Investigator. Aliquots from the PK, biomarker and anti-drug antibody samples may be retained as back-up for additional testing as necessary. Subjects will be in a seated or supine position during blood collection. Full clinical safety lab draws will be collected at Screening and on Days 0, 7, 14, 21, 28, 33, 42, 56, 84 and 112. The total blood draw for each subject who completes the study at Day 112, will be approximately 433 mL. Please refer to the Laboratory Manual for more information.

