**Virology**

---

- Hepatitis C
  - Hepatitis B
  - HIV
  - VZV
  - Tetanus
- 

ALT = alanine aminotransferase; AST = aspartate aminotransferase; CBC = complete blood count; BUN = blood urea nitrogen; HIV = human immunodeficiency virus; LDH = lactate dehydrogenase; VZV = varicella-zoster virus

Abnormalities in clinical laboratory tests that are considered clinically significant are to be recorded on the AE electronic case report form (eCRF) page. Laboratory results will be graded using the NCI CTCAE, Version 4.03. If laboratory values constitute part of an event that meets criteria defining it as serious, the event (and associated laboratory values) must be reported as an SAE (see [Section 11.3.1](#)).

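### Section 12.5 flags uncoded laboratory results in the listings against local-laboratory limits although testing is central, and its laboratory incidence and worst-grade summaries take no account of baseline grade

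*Protocol*

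**What the plan says.** All references are to the latest protocol text; the SAP is not available.

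- **Who runs the tests.** Section 6.7 says that laboratory testing, including hematology, chemistry and urinalysis, "will be performed using established methods by a central laboratory".
- **Limits for the listings, synopsis.** Variables that are not coded are shown as "below, within, and above the normal limits of the central laboratory".
- **Limits for the listings, Section 12.5.** The same rule appears with a different laboratory: "Results for variables that are not coded will be presented in the listings" as "below, within, and above the normal limits of the local laboratory".
- **Grading.** Below Table 3 in Section 6.7: "Laboratory results will be graded using the NCI CTCAE, Version 4.03".
- **Summaries.** Section 12.5 plans a summary of laboratory results by cohort and an incidence of laboratory abnormalities, and adds: "The worst on-study grade after the first dose of study drug will be summarized". It names no baseline grade, change or shift for laboratory data.
- **Contrast in the same section.** "Vital sign measurements and change from baseline will be summarized at each scheduled time point by cohort". ECG parameters also get change from baseline, and ECG categories get shift tables from pre-dose.
- **Role of the data.** The synopsis gives the primary endpoint as "AEs and clinical (safety) laboratory tests". Section 4.2 lists laboratory tests as one of five components of the primary safety measure.

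**The concern.** There are two separate defects in one section.

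The first is a contradiction about reference limits. Limits belong to the assay and laboratory that produced the result. Followed literally, Section 12.5 would flag central results against ranges from laboratories that did not run the test. For variables without a CTCAE grade, that flag may be the only abnormality classification the section provides.

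The second is the missing baseline. The study is open-label with no control, so the subject's own pre-dose value is the natural reference. Section 5.2 lets subjects enter on prednisone or equivalent up to 1 mg/kg/day, and on stable azathioprine, mycophenolate mofetil or cyclosporine. Some abnormal Day 0 values are therefore plausible. A worst post-dose grade that ignores the starting grade puts a subject who entered at Grade 1 and stayed there in the same cell as a subject who moved from normal to Grade 1. At stake is how the safety tables read with 8 subjects per cohort, where one or two subjects change the impression.

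**Working it through.** **Step 1: the limits, side by side.**

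| Place | Subject | Laboratory named |
|---|---|---|
| Section 6.7 | who performs the tests | central |
| Synopsis, statistical methods | limits for listing flags | central |
| Section 12.5 | limits for listing flags | local |

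The last two rows state the same rule, so both cannot be followed. Section 6.7 decides between them: results come from a central laboratory, and no passage provides for local safety assays or for collecting local reference ranges.

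**Step 2: how far the wrong word reaches.** The sentence in Section 12.5 is limited twice, to variables that are not coded and to listings. The term is not defined; I take it to mean not graded by CTCAE. On that reading it could cover ESR, C-reactive protein, LDH and BUN, which are in Table 3 and have no term in the Investigations part of the CTCAE appendix (later parts of the appendix are not shown). Graded tests are not covered. Many grades do depend on an upper or lower limit of normal, and Section 12.5 does not say whose, but no passage assigns local limits to grading.

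**Step 3: baseline handling within Section 12.5.**

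| Data type | Baseline reference named |
|---|---|
| Vital signs | change from baseline |
| ECG | change from baseline, and shift from pre-dose |
| Laboratory | none |

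The data for a baseline reference exist. Section 6.7 schedules draws at Screening, Day 0 and nine later days (7, 14, 21, 28, 33, 42, 56, 84, 112), and Section 7.2 places the Day 0 draw before the first dose.

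**Step 4: possible size of the overcount.** The plan states no figure to reproduce. As an illustration, let q be the share of subjects already at Grade 1 or above on one analyte at baseline. Assume they stay there, the drug has no effect, no new abnormality arises, and subjects are independent. For a cohort of 8:

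- expected number counted = 8q
- probability that at least one is counted = 1 − (1 − q)^8

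| q (assumed) | 8q | 1 − (1 − q)^8 |
|---|---|---|
| 5% | 0.4 | 34% |
| 10% | 0.8 | 57% |
| 25% | 2 | 90% |
| 50% | 4 | 99.6% |

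Under the same assumptions, a count restricted to worsening from baseline is 0 in every row. The values of q are mine; the documents give none.

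**The case against.** The strongest reply has four parts.

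**Scope of the local-limits sentence.** A reader might infer that the laboratory part of the primary endpoint is misclassified, or that about 10 sites mean about 10 sets of limits for one assay. Neither follows. The sentence governs only listing flags for uncoded variables, not the incidence table, the worst-grade summary or CTCAE grading. With testing done centrally, multiple sets of limits would arise only from the wording slip. Nor are laboratory tests half of the endpoint in Section 4.2, where they are one of five components. This part of the reply stands in full.

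**Baseline is not absent from the protocol.** The synopsis summarizes laboratory results by time point, so pre-dose and post-dose summaries appear together. Section 12.1 lists all data by subject. Section 11.4.1 excepts values consistent with those before entry from AE reporting. Some CTCAE grades, such as creatinine, use baseline directly. This stands: a true worsening can be found by reading the listings. It does not repair the summary table, which counts the very values that Section 11.4.1 sets aside.

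**A worst post-dose grade is a valid description.** It is labelled on-study, not treatment-emergent or drug-related. Also correct. The table is incomplete rather than wrong.

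**Shift tables are usually SAP matter.** Section 12.3 leaves detailed methodology to the SAP, which may well add one. That is a fair reason to treat the second part as a modest request. It does not remove the point, because Section 12.5 itself specifies baseline handling by data type and leaves it out only for laboratory tests.

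**Conclusion.** Both parts hold, within limits. The central/local contradiction is certain from the text and affects flags in listings of uncoded laboratory variables. How many flags would change cannot be computed, since no reference ranges are given. The baseline gap is also plain from the text: as written, the laboratory incidence and worst-grade summaries cannot separate abnormalities present before dosing from those that emerged or worsened. Any overcount depends on a Day 0 abnormality rate that the documents do not state. The range of 0.4 to 4 of 8 subjects per analyte rests on an assumed 5% to 50%, persistence after dosing and no drug effect. The evidence supports a correction and one added table. It does not support a claim that the primary endpoint is misclassified or that toxicity will be overstated by a known amount.

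**What to change.** 1. In Section 12.5, replace local laboratory with central laboratory, so that it agrees with the synopsis and Section 6.7.
2. In Section 12.5 or the SAP, add a table per cohort of baseline grade (last pre-dose value) against worst post-dose CTCAE grade. For analytes whose grade can be set by a multiple of baseline, such as creatinine, assign the baseline grade from the limit-of-normal criterion.
3. Report the number of subjects whose grade worsens by at least one from baseline, and keep the planned worst-grade table as supportive.

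The cost is one word and one table per cohort. No extra sampling is needed, because Screening and Day 0 draws are already scheduled. Section 12 has the SAP finalized before database lock, so both changes can be made by then.
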